1. REPORTING & ANALYSIS PLAN SYNOPSIS

Overview	Key Elements of the RAP
Purpose	
 The purpose of this reporting and analysis plan (RAP) is to describe the analyses to be included in the Clinical Study Report for Protocol TAF116564. This document will be provided to the study team members to convey the content of the Statistical Analysis Complete (SAC) deliverables.
Protocol	
 This RAP is based on the original protocol amendment 5 (15-JUL-2015) of study TAF116564 [GSK Document Number: 2012N152563_01] and eCRF Version 3.0.
Primary Objective	
 To investigate the occurrence of clinically relevant haemolysis in adult subjects with P. vivax.
Primary Endpoint	
 Occurrence of clinically relevant haemolysis in all subjects; defined as, a decrease in haemoglobin of $\geq 30\%$ or >30 g/L (>3 g/dL) from baseline; or, an overall drop in haemoglobin below 60 g/L (6.0 g/dL).
Study Design	
 Study TAF116564 is a prospective, double-blind, double-dummy, multicenter, comparative study. The duration of the study is 180 days, including screening and randomization to treatment (Day 1), three in-hospital days (Days 1-3), four out-patient visits while on treatment with study medication (Days 5, 8, 11 and 15) and seven follow-up visits (Days 22, 29, 60, 90, 120, 150 and 180). A total of 300 subjects will be randomized 2:1 to receive TQ/CQ or the active comparator PQ/CQ.
Planned Analyses	
 No interim analysis is planned. All decisions regarding final analysis, as defined in this RAP document, will be made prior to Database Freeze (unblinding) of the study data.
Analysis Populations	
 Safety Population: all randomized subjects who received at least one dose of blinded study medication. If subjects receive a treatment different to their randomized treatment, they will be analyzed according to the treatment actually received. This will be the primary population for all safety analyses and data presentations. Microbiologic Intent to Treat (mITT) Population: all randomized subjects who receive at least one dose of blinded study medication and have microscopically-confirmed vivax parasitemia. Subjects will be analyzed according to their randomized treatment. This population will be the primary population for all efficacy analyses. Per Protocol (PP) Population: all subjects in the mITT population for whom there were no major protocol violations. This population will be used for sensitivity/supporting analyses of efficacy data only. Ophthalmic Safety Population: all subjects in the safety population who have results from any eye assessments.
Hypothesis	
 There will be no hypotheses tested in this study.

Overview	Key Elements of the RAP
Primary Analyses	
 The proportion of subjects with clinically relevant haemolysis in each treatment group will be presented together with a confidence interval based on the Wilson score. The difference between treatment groups in the proportion of subjects with clinically relevant haemolysis in each treatment group will be presented together with a confidence interval based on the Newcombe method
Secondary Analyses	
 All survival efficacy endpoints, e.g. time to relapse, relapse as a success/failure will be analysed by Cox proportional hazards and Kaplan Meier methodology. Binary endpoints, e.g. relapse/no relapse at 6 months, will be analysed by logistic regression. Other secondary efficacy endpoints will be summarised descriptively by treatment group. Safety data will be presented in tabular format and summarized descriptively according to GSK's Integrated Data Standards Library (IDSL) standards. Pharmacokinetic analyses will be detailed in a separate document. Pharmacogenetic data will be summarised and an exact logistic regression model will be used to assess the effect of derived CYP2D6 metabolizer class within treatment arm on relapse efficacy six months post-dosing. Healthcare resource use of P. vivax relapses and haemolysis events will be summarised descriptively.

1.1. RAP Amendments

RAP Section	Amendment Details
Reporting and Analysis Plan_StudyTAF116564_Final [05-AUG-2016]	
Reporting and Analysis Plan_StudyTAF116564_Final_Amend 1 [21-FEB-2017]	
1.0, 4, 8.1.2, 10, 13.14.4, 13.14.8	Removal of Pharmacogenetics population – not required. mITT and Safety populations are sufficient as CYP2D6 and G6PD genotyping are collected under the main Informed Consent.
7.1.2	Correction of Newcombe upper confidence limit equation
8.1.2, 13.14.4, 13.14.5, 13.14.11	
Secondary Statistical Analyses: Re-design of efficacy analysis tables to display Cox Proportional Hazard and Kaplan-Meier results in one display
 
Sensitivity Analyses: By Genetic Classification: re-design of analyses to look at heterologous and homologous infections separately with new censoring rules
 
Sensitivity Analyses: Chloroquine Supply: Additional analyses included to

RAP Section	Amendment Details
	investigate the effect of chloroquine supplied before and after a cut-off date Secondary Statistical Analyses: Early Failures: Inclusion of category of early failures where the parasite genetics are missing; listing added Secondary Statistical Analyses: CYP2D6: minor changes to the output statistics
8.2.2, 13.14.6	Urine concentration change from baseline removed as no continuous urinalysis data is collected
13.6.3	Laboratory Parameters: Standard text on handling non-detectable lab values added
13.6.4	Relapse-free efficacy at 6 months and 4 months definitions: censoring added to account for subjects that take a concomitant medication with anti-malarial action prior to clearance plus clarification to the time periods assessed for 4 months Genetic classification of relapse definition: added to include censoring rules Recrudescence definition: clearance definition updated in line with other efficacy endpoints Fever clearance definition: updated to reflect Time and Events schedule of temperature collection
13.10.1	Addition of chloroquine supply covariate
Various	Typographical errors corrected

2. SUMMARY OF KEY PROTOCOL INFORMATION

2.1. Changes to the Protocol Defined Statistical Analysis Plan

There are changes or deviations to the originally planned statistical analysis specified in the protocol amendment 5 (Dated: 15-JUL-2015). In the protocol, the primary objectives are:

1. To investigate the occurrence of clinically relevant haemolysis in adult subjects with *P. vivax*.
2. The incidence of haemolysis in the subgroup of female patients with moderate (40-70%) G6PD activity is of particular interest.

Due to difficulties in recruitment of G6PD deficient subjects, this subgroup of subjects will be limited in number and therefore the incidence in this subgroup will not be

estimated. Therefore the only primary objective is the treatment difference of the occurrence of clinically relevant haemolysis in adult subjects with *P. vivax*.

Any subjects who are G6PD deficient will be included in the main analyses unless described otherwise.

The protocol defined subject study completion as: the subject meets all inclusion/exclusion criteria, is considered compliant with all study medication, completes the 3 day hospital stay, and attends the Day 180 visit; however a more appropriate definition of “a subject that does not withdraw from the study and attends the Day 180 visit” will be used.

The protocol specified that data will be allocated to visit windows using actual visit dates rather than nominal visit numbers, however to remain consistent with study TAF112582, nominal visit will be used. Further details are given in Section 13.3.

Duration of exposure will not be calculated as specified in the protocol as date of last dose of active study medication – date of first dose of study medication + 1, because the date of last dose is not collected. Compliance and exposure will be presented as described in Section 6.6.

Adverse events that are considered to be gastrointestinal-related will not be reported separately as earlier studies have shown these not to be Adverse Events of special interest.

The protocol stated that Fisher’s Exact analyses will be performed for the missing=failure analysis of relapse-free efficacy (see Section 8.1.2), but as the number of subjects relapse-free is expected to be large enough, logistic regression will be performed to allow the inclusion of important covariates.

Time to event endpoints will be analysed using Cox proportional hazards methodology, in addition to the Kaplan-Meier methodology described in the protocol.

[figure not shown]
The effect of CYP2D6 metabolism on relapse efficacy within treatment arm and ophthalmic assessments as safety endpoints were not explicitly specified in the protocol as objectives and endpoints. They have been added to the list in Section 2.2.

2.2. Study Objective(s) and Endpoint(s)

Objectives	Endpoints
Primary Objectives	Primary Endpoints

 To investigate the occurrence of clinically relevant haemolysis in adult subjects with P. vivax. 	
 Occurrence of clinically relevant haemolysis in all subjects; defined as, a decrease in haemoglobin of $\geq 30\%$ or >30 g/L (>3 g/dL) from baseline; or, an overall drop in haemoglobin below 60 g/L (6.0 g/dL).
Secondary Objectives	Second Endpoints

 To compare the clinical and parasitological efficacy, safety and tolerability of tafenoquine to primaquine as a radical cure for 	
 Relapse-free efficacy six months post-dosing Relapse-free efficacy four months post-dosing Time to relapse

Objectives	Endpoints

adult subjects with P. vivax malaria when co-administered with chloroquine.
	
 • Parasite clearance time • Fever clearance time • Gametocyte clearance time • Recrudescence, defined as any P. vivax parasitemia occurring on or before Day 32 (i.e. blood stage treatment failure). • Incidence of genetically homologous and genetically heterologous P. vivax infections (determined by PCR) • Safety evaluation of data from clinical laboratory tests, urinalysis, spontaneous/elicited adverse event reporting, ECGs and vital signs in all subjects who received at least one dose of study medication. • Incidence of P. falciparum malaria • Ophthalmic assessments

 • To characterize the socioeconomic impact of P. vivax relapse. 	
 • Characterization of healthcare resource use and socio-economic impact of P. vivax relapses and adverse events caused by treatment to prevent P. vivax relapses, especially haemolytic anemia.

 • To evaluate the pharmacokinetics of tafenoquine in the treatment of adult subjects with P. vivax malaria. 	
 • Population PK parameters for tafenoquine including but not limited to oral clearance (CL/F) and volume of distribution (V/F)

 • To characterize the pharmacokinetic/ pharmacodynamic relationship in this study population. 	
 • PK and selected PD endpoints (e.g. relapse-free efficacy, change in methaemoglobin) if appropriate

 • To evaluate the effect of CYP2D6 metabolism on relapse efficacy within treatment arm 	
 • Relapse-free efficacy six months post-dosing

2.3. Study Design

Overview of Study Design and Key Features	
	
corresponding placebo for treatment of the liver stage of infection.
 
 • At the Day 1 visit subjects will be screened for G6PD deficiency by a quantitative assay and the result will be determined as a percentage of the predetermined median enzyme activity of the site. Female subjects must have a minimum G6PD assay value of 40% to be enrolled, and male subjects must have a minimum G6PD assay value of 70% to be enrolled. • Parasitological assessments will be carried out at each visit in the follow up period. • Other assessments include healthcare resource use and socio-economic data, ophthalmic assessments (selected investigator centres only), vital signs, ECGs, laboratory assessments and blood samples for pharmacokinetic and pharmacodynamic analyses.
Dosing	
 • All subjects will receive CQ on Study Days 1 to 3, followed by TQ or PQ and matching placebo beginning on Study Day 1 or 2. Tafenoquine, or matching placebo, will be given as a single, 300mg dose. Subjects will receive PQ (15mg once daily) or matching placebo for 14 days.
Treatment Assignment	
 • A total of 300 subjects (250 with normal G6PD enzyme activity and 50 females with moderate (40-70%) G6PD enzyme activity) were to be randomized 2:1 to receive TQ or the active comparator PQ. • GSK RANDALL NG will be used to generate randomisation schedules. • Treatment allocation will occur by centralised randomisation using GSK RAMOS, accessed by sites via an Interactive Voice Recognition System (IVRS)
Interim Analysis	
 • No formal interim analyses are planned for this study.
Sample Size	
 • A sample size of 300 (250 with normal G6PD enzyme activity and 50 females with moderate (40-70%) G6PD enzyme activity) was based on the regulatory requirement to obtain an appropriate total safety database in subjects treated with TQ/CQ at the selected dose, given that subjects are randomized to TQ/CQ: PQ/CQ on a 2:1 ratio.

2.4. Statistical Hypotheses

There will be no hypotheses tested in this study.

3. PLANNED ANALYSES

3.1. Interim Analyses

No formal interim analyses are planned for this study.

3.2. Final Analyses

The final planned primary analyses will be performed after the completion of the following sequential steps:

- All subjects have completed (or withdrawn) from the study.
- All required database cleaning activities have been completed and final database release and database freeze has been declared by Data Management.
- All criteria for unblinding the randomisation codes have been met.
- Randomisation codes have been distributed according to RandAll NG procedures.
- An IDMC will be utilized in this study to ensure external objective medical and/or statistical review of safety issues in order to protect the ethical and safety interests of subjects and to protect the scientific validity of the study.

4. ANALYSIS POPULATIONS

Population	Definition / Criteria	Analyses Evaluated
Safety	
 • All randomized subjects who received at least one dose of blinded study medication. • Subjects will be analysed according to the treatment a subject actually received. 	
 • Primary population for all safety analyses and data presentations
Microbiologic-Intent-To-Treat (mITT)	
 • All randomized subjects who receive at least one dose of blinded study medication and have microscopically-confirmed vivax parasitemia at Baseline. • Subjects will be analysed according to the treatment a subject was randomized to. 	
 • Primary population for all efficacy analyses
Per-Protocol (PP)	
 • All subjects in the mITT population for whom there were no major protocol violations. 	
 • Sensitivity/ supporting analyses of efficacy data only
Ophthalmic Safety	
 • All subjects in the safety population who have results from any eye assessments. 	
 • Analyses of ophthalmic endpoints

NOTES :

- Please refer to [Appendix 14](#): List of Data Displays which details the population to be used for each displays being generated.
- PK and PK/PD data are being handled outside of this RAP so PK and PK/PD populations are not included in this table.

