4.4. Premature Withdrawal of Study Medication

If a subject prematurely discontinues from blinded study medication, the reason for withdrawal from medication should be recorded in the eCRF. As useful safety and efficacy information can still be obtained for these patients, the investigator should continue following subjects for all protocol assessments, up to and including day 180. The subject should be offered/given appropriate rescue medication as detailed in [Section 5.6.1.2](#) if they get a recurrence of malaria due to inability to take blinded study medication.

Subjects who withdraw from open label CQ (and prior to receiving blinded study medication) will not continue in the study and should be offered alternative treatment in accordance with site (local) or national treatment guidelines for *P. vivax* malaria. These subjects should be followed up until resolution of the malaria infection.

In addition, subjects should discontinue taking study medication if they meet any of the following criteria:

- Any grade 4 AE or toxicity in the absence of compelling evidence that the AE is not related to study medication

- Clinically significant laboratory results considered by the investigator to warrant withdrawal from the study
- QT stopping criteria as defined below:
 - QTcF > 500msec
 - Uncorrected QT > 600msec

These criteria should be based on the average QTcF value of triplicate ECGs. For example, if an ECG demonstrates a prolonged QT interval, obtain two more ECGs over a brief period, and then use the averaged QTcF values of the three ECGs to determine whether the patient should be discontinued from the study.

- For subjects with underlying Bundle Branch Block, the criterion is ≥ 530 msec.
- Liver chemistry stopping criteria as specified in Section 6.4.1
- Given the hemolytic potential of TQ and PQ in subjects with G6PD deficiency, study specific hemoglobin stopping criteria will be employed. Refer to Section 6.4.2 for details.

When QT or hematologic stopping criteria are met, this must be promptly reported by the investigator to GSK (see Section 6.4.11)

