5. STUDY TREATMENTS

5.1. Investigational Product and Other Study Treatment

Throughout the protocol, study treatments will be defined and described as follows:

- "Study medication" refers to all drugs and placebos used in the study
- "Blinded study medication" refers to tafenoquine, primaquine and the corresponding placebos

The contents of the study medication labels will be in accordance with all applicable regulatory requirements. All study medication is being supplied by GlaxoSmithKline.

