Pharmacokinetic Assessments																
PK/PD Sampling ^u		X	X		X		X		X	X					X	
Investigational Product																
Dispense Open Label Chloroquine	X	X	X													
Dispense Blinded Study Medication	X ^v	X ^v														
Treatment Compliance Int. - Invest.	X	X	X	X	X	X	X									
IVRS Registration	X															

- a All subjects must remain hospitalized for Days 1 through 3.
- b Subjects who relapse will continue to be monitored for safety and efficacy at all scheduled visits through day 180. Relapse is defined by a positive blood smear with or without vivax symptoms.
- c If subjects withdraw from blinded study medication, all scheduled follow-up visits should be performed to conduct safety assessments up to and including Day 180.
- d Visit Day 1 includes all screening procedures and the first day of treatment with study medication.
- e Includes medical, disease and therapy histories.
- f Blood smears are to be taken twice a day, 6-12 hours apart for the first 3 days, or until 2 consecutive negative thick blood smears are obtained.
- g Vital signs include height and weight (screening only), blood pressure, temperature, heart rate and respiratory rate. Vital signs are to be performed twice a day on Days 1 through 3, at least 4 hours apart, and immediately prior to PK measurements.
- h ECGs are to be performed at screening (in triplicate), 12 hours after the first dose of blinded study medication, and on Day 29.
- i Adverse events are recorded from the time of the first dose of study medication.
- j Serious adverse events are recorded from the time of consent in order to fulfil international regulatory requirements.
- k G6PD phenotyping to be performed by quantitative spectrophotometric analysis. One or more G6PD rapid point of care tests may be performed at baseline (Day 1) only.
- l Only if Day 90 ophthalmological exam shows abnormalities.
- m Hematology includes hemoglobin, hematocrit, red blood cell/white blood cell/platelet counts, mean cell volume, white blood cell differential and reticulocyte count.

- n Hematology and clinical chemistry on Day 3 must be reviewed prior to discharge from the hospital.
- o Clinical Chemistry includes CPK, BUN, serum creatinine, total and indirect bilirubin and liver clinical chemistry.
- p Mid-stream urine will be analyzed for protein, glucose, ketones, bilirubin, blood, nitrites, urobilinogen and leukocyte esterase by dipstick method.

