8.2. Safety Analyses

The safety analyses will be based on the Safety population, unless otherwise specified.

Details of data displays are presented in [Appendix 14: List of Data Displays](#).

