8.2.1. Overview of Planned Adverse Events Analyses

Counting of AEs will be based on the number of subjects – not the number of AEs. For example, if a subject reports the same AE on three occasions within the relevant time interval, that AE will only be counted once. If a subject experiences the same AE (i.e. same preferred term) more than once, they are counted only once under the count for the preferred term. If a subject experiences more than one AE in a particular SOC, they will only be included once in the count for the SOC, but will appear in the count for each appropriate preferred term within the SOC. Therefore, the sum of the numbers of subjects with each preferred term event within a SOC may exceed the total number of subjects with at least one event. For the summary of AEs by maximum intensity, subjects who experience the same event several times with different intensity will only be counted once with the maximum intensity.

Only treatment emergent AEs (TEAEs) will be presented as all subjects receive study medication on Study Day 1. TEAEs are defined as AEs with an onset date and time on or after that of the start of first dose of study medication (including CQ)

The occurrence of *P. vivax* malaria and any associated signs and symptoms are recorded as Disease Related Events (DREs) and will not be included in the AE data displays, but will be listed separately.

Adverse Events will be summarized by treatment group and as specified below and in [Appendix 14: List of Data Displays](#) and presented in order of descending frequency. [Table 2](#) provides an overview of the planned analyses, with further details of data displays being presented in [Appendix 14: List of Data Displays](#).

Table 2 Overview of Planned Adverse Event Analyses

Endpoint / Parameter/ Display Type	Absolute		
	Summary		Individual
	T	F	L
Adverse Events (AEs)			
All AEs			Y ¹
All Treatment Emergent AEs by SOC	Y		
All Treatment Emergent AEs by PT	Y		
Drug-related TEAE by PT	Y		
TEAEs by maximum intensity	Y		
Common (>=5% in any treatment group) TEAEs by PT	Y	Y ²	
Common (>=5% in any treatment group) Non-serious TEAEs by SOC and PT – number of subjects and occurrences	Y		
TEAEs by month of onset	Y		
Subject numbers for individual AEs			Y
Relationship between AE SOC, PTs and verbatim text			Y
Serious and Other Significant AEs			
Fatal TEAEs by PT	Y		Y
Serious TEAEs ³	Y		Y
Drug related serious TEAEs by PT	Y		
Drug related fatal serious TEAEs by PT	Y		

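### Randomised subjects who stop after chloroquine alone fall within the stated safety endpoint, but appear in no planned disposition, AE or SAE table or listing

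*Supplement*

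**What the plan says.** RAP Amendment 1, section 2.2, lists among the secondary endpoints a safety evaluation of laboratory tests, urinalysis, adverse events, "ECGs and vital signs in all subjects who received at least one dose of study medication". Section 2 of protocol Amendment 5 has the same endpoint. Protocol section 5.1 says that study medication "refers to all drugs and placebos used in the study", and separately defines blinded study medication as tafenoquine, primaquine and their placebos. Chloroquine is therefore study medication, but not blinded study medication.

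The collection and counting rules follow the wider term. A footnote to the protocol's Time and Events table says "Adverse events are recorded from the time of the first dose of study medication". RAP 8.2.1 treats an AE as treatment-emergent if its onset is "on or after that of the start of first dose of study medication (including CQ").

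The analysis population follows the narrower term. RAP section 4 defines the Safety population as "All randomized subjects who received at least one dose of blinded study medication" and gives its use as "Primary population for all safety analyses and data presentations". RAP 8.2 repeats the default: "The safety analyses will be based on the Safety population, unless otherwise specified". Protocol 8.3.1 has the same definition.

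The protocol also foresees the subjects who fall between the two. Section 4.4 says "Subjects who withdraw from open label CQ (and prior to receiving blinded study medication) will not continue in the study", and has them followed until the malaria resolves.

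**The concern.** The endpoint and the population that reports it are not the same set. A randomised subject who takes chloroquine and leaves before any blinded dose is inside the endpoint and has AEs collected, but is outside the Safety population. If the displays all use that population, the plan's own rule removes collected events from the planned safety output.

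Safety is the main purpose of this trial, and results are labelled TQ+CQ and PQ+CQ, so chloroquine belongs to the regimen being described. A single unlisted SAE or death would matter to a reader of the study report. As planned, the disposition and AE displays would not even show that there were no such subjects.

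**Working it through.** The plan states no figure on this point, so the check compares texts. A small calculation follows, for scale only.

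**1. Who is covered by each rule**

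| Rule | Source | Chloroquine-only subject covered? |
|---|---|---|
| Safety endpoint | RAP 2.2; protocol 2 | Yes |
| AE collection | Protocol Table 2 footnote | Yes |
| Treatment-emergent definition | RAP 8.2.1, 13.6.3 | Yes |
| Baseline and Study Day 1 | RAP 13.5.2.1, 13.6.1 | Yes |
| Safety population | RAP 4; protocol 8.3.1 | No |

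RAP 2.1, which lists departures from the protocol, does not narrow the endpoint.

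**2. Can such a subject arise?** Protocol 3.3 puts randomisation on Day 1. Both dosing tables in protocol 5.1.8 show blinded drug from Day 2, and the notes beneath them, with a footnote to Table 2, allow Day 1 or Day 2. A Day 2 starter randomised on Day 1 therefore has an interval on chloroquine alone. Protocol 4.4 provides for withdrawal in that interval. Section 5.1.8 also takes off study medication a subject who vomits two doses in sequence.

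**3. Does any planned display show them?** From the population column of RAP Appendix 14:
- Table 1.3 (disposition), Tables 3.3-3.21 (AEs, SAEs, fatal events, withdrawals) and Listings 2 and 9-13 are all on Safety.
- Listing 5, meant to show subjects excluded from any population, is itself on Safety, so it cannot show anyone excluded from Safety.
- The displays on a wider set are Tables 1.1, 1.6 and 1.22 and Listing 20 (all screened) and Tables 5.1 and 5.2 (all randomised). They cover population counts, screen failures, the G6PD test comparison and genetic consent. None carries AEs or reasons for leaving after randomisation.
- RAP 13.6.2 assigns zero doses to randomised subjects without a treatment start date, but the compliance display (Table 1.21) is on Safety too.

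**4. Scale, under assumed rates.** With N randomised and an assumed proportion r stopping after chloroquine only, the expected number is N × r and the chance of at least one is 1 − (1 − r)^N. The meta-analysis plan, section 3, gives N = 251 (300 were planned).

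| r (assumed) | Expected, N = 251 | P(at least one), N = 251 | Expected, N = 300 | P(at least one), N = 300 |
|---|---|---|---|---|
| 0.2% | 0.5 | 0.40 | 0.6 | 0.45 |
| 0.5% | 1.3 | 0.72 | 1.5 | 0.78 |
| 1% | 2.5 | 0.92 | 3.0 | 0.95 |
| 3% | 7.5 | >0.99 | 9.0 | >0.99 |

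One subject with an SAE would be 1/251 = 0.4% of those randomised. No document supports any particular r.

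**The case against.** The strongest reply is that the population was fixed on purpose. Protocol 8.3.4.2 bases all safety endpoints on the Safety population, and protocol 8.3.1 defines that by a blinded dose, so the endpoint bullet may simply be loosely worded. A subject who took neither tafenoquine nor primaquine has no place in an as-treated comparison of the two. This stands, and it is why the Safety population should remain for every comparison. It does not explain why disposition and the list of excluded subjects should be confined to that population, or why collected events should have no listing.

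A reader might infer more than the documents support, in four ways:
- **That the events are reported nowhere.** Protocol 6.4.9 sends SAEs to the sponsor within 24 hours, an independent committee monitors safety, and RAP 13.6.3 says AEs reported after enrolment are documented. The gap is in the planned RAP displays.
- **That subjects are dropped because their events were severe.** Protocol 4.3 allows withdrawal for consent, loss to follow-up, deviation or investigator decision. Exclusion can follow from an event but need not.
- **That chloroquine QT effects are being hidden.** The first scheduled ECG after screening comes 12 hours after the first blinded dose, so no routine on-treatment ECG falls in the chloroquine-only interval. A withdrawal-visit ECG is possible.
- **That the treatment comparison is biased.** Before the first blinded dose no subject has taken either drug and assignment is masked. Post-baseline haematology is first scheduled on Day 3. Neither the comparison nor the haemolysis endpoint is touched.

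The exposed group may also be very small. Day 1 starters may have no chloroquine-only interval, and the meta-analysis plan, section 8.2, allows randomisation on Day 2, although this protocol says Day 1. The number of randomised subjects outside Safety could be found by subtracting Table 1.1 from Table 5.1, but that would not separate chloroquine-only subjects from those who took nothing, and would show no events.

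**Conclusion.** The mismatch is real and sits in the current RAP and protocol. The safety endpoint and the treatment-emergent rule include chloroquine-only subjects, while the planned disposition, AE, SAE, fatal-event and withdrawal tables and listings leave them out. The consequence is limited to incomplete reporting. The number affected is not given, is probably small and may be zero; the range of about 0.5 to 7.5 of 251 rests wholly on assumed rates of 0.2% to 3%. The tafenoquine versus primaquine and haemolysis results do not change. The documents do not support a claim that early toxicity has been understated by any known amount. The point is worth acting on because the repair is cheap and uses data already collected.

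**What to change.** 1. Keep the Safety population for all treatment comparisons, including haemolysis and Tables 3.3-3.21. These need no rerun.
2. In RAP 13.14, move Table 1.3 and Listings 2 and 5 to all randomised subjects, a set already used for Tables 5.1 and 5.2. Show chloroquine-only subjects under their randomised arm.
3. Add one supplementary display for randomised subjects who received chloroquine but no blinded dose: their number, and a listing of their AEs, SAEs and deaths. If there are none, the display should say so.
4. Reconcile RAP 2.2 with RAP 4. Either word the endpoint for blinded study medication and name the supplementary listing as the place for the others, or keep the endpoint wording and state that the listing completes it. Record the choice in RAP 2.1.

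The cost is a few lines of RAP text, a changed population filter on three displays and one short listing. No new data are needed, because AEs are collected from the first chloroquine dose. Nothing about dosing, withdrawal or follow-up changes.
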